This is a Prospective Randomized Controlled trial that will be conducted at the National Cancer Institute. All patients who are eligible for the study will be included and randomized into 3 equal groups.

PATIENTS AND METHODS

After approval from the Ethics Committee at the National Cancer Institute, Cairo University, and obtaining written informed consent, eighty-one patients with thoracic segmental pain due to metastasis, unresponsive to conventional therapy and meeting the inclusion criteria will be randomly assigned to either one of the two types of treatment, PRF or TRF lesioning of the DRG or the control group. Patients will be carefully evaluated for neurologic deficits and side effects. Assessment of pain will be done at baseline then at 1, 3, 6 months after the procedure. Randomization will be done using randomized permuted block design. Randomization list will be generated through random.org online site.

INCLUSION CRITERIA:

1. A greater than 6-month history of segmental pain of thoracic vertebral body metastasis origin.

2. Unsatisfactory pain control with oral pharmacotherapy including strong opioid with VAS >5 .
3. Absence of a chronic or progressive motor deficit.
4. Absence of significant sensory deficit.
5. No indication for percutaneous or open surgical intervention.
6. Magnetic resonance imaging and Computed Tomography evidence of thoracic involvement.
7. ASA status of II to III .
8. Age \geq 18 .
9. Body mass index (BMI) :less than forty and more than twenty .
10. Informed consent

EXCLUSION CRITERIA:

1. Known sensitivity or contraindication to injected materials: local anesthetics.
2. History of psychological disorders.
3. Evidence of significant neurological deficit.
4. Inability to lie prone.
5. Local contraindication to procedure e.g. local sepsis at the site of intervention, coagulopathy.
6. Patient refusal.

Patients will be randomly assigned and divided into 3 equal comparable groups. Before the procedure, laboratory investigations, Dorsal X-ray, CT and MRI will be done. All Patients will be interviewed and examined by physicians trained in interventional pain management. Patients will be carefully assessed on physical exam for sensory, motor, or reflex deficit and

carefully documented. Patients will be informed about the technique of the blocks, and written informed consents will be obtained.

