According to studies ^(13,15,16) , to see a significant reduction in VAS defined as at least 50% reduction, ODI, QLQ-C30 and QLQ-BM22 score ($P < 0.01$) with a background standard deviation of 1.0, significance level of 0.05 and power of a test of 80%, minimum number of patients needed would be 25 per group. Because difference in VAS , ODI, QLQ-C30 and QLQ-BM22 score will be more evidenced with control group, the number needed would be much smaller , so the total number needed in the present study would be 69 patients that will be randomized into 3 equal groups. For non-parametric correction, we increased the number to 27 patients for each group.

2- Statistical analysis plan:

Data will be analyzed using SPSS version 18.0. Numerical data will be presented as mean, standard deviation or median and range as appropriate. Categorical data will be presented as numbers and proportions. Mixed models ANOVA will be used to show effect of time on pain score and also to evaluate group interaction. Non-parametric tests ; Friedman's test will be used if data did not show normal distribution. Significance level will be considered at 0.05.

REFERENCES

1. **Smith HS.** and **Barkin RL**, Painful boney metastases, American Journal of Therapeutics , 2014 ;21(2):106-130.
2. **Patrick W.**, Bone Cancer Pain: From Mechanism to Therapy, Current opinion in supportive and palliative care 2014 ; 8(2): 83–90.
4. **Bhatia A.** , Questions Regarding "Pulsed Radiofrequency for Chronic Intractable Lumbosacral Radicular Pain: A Six-Month Cohort Study", Pain Medicine 2016; 17(5):989.
6. **R. Carter W. Jones III**, Neuroinflammatory effects of Radiofrequency, European Journal of Pain 2014; 18 :149-150.
7. **Zeldin A. and Ioscovich A.**, Pulsed Radiofrequency for Metastatic Pain Treatment, Pain Physician 2008; 11:921-922 .

8. **Young-Chang P. Arai, Makoto N., Yoshihiro Y., Maki A., Miki K., Chiharu S., Akiko K., Kazuyo K., and Tatsunori I.,** Dorsal Root Ganglion Pulsed Radiofrequency for the Management of Intractable Vertebral Metastatic Pain: A Case Series, *Pain Medicine* 2015; 16:1007 – 1012.

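### The choice of main analysis depends on an undefined normality check on the data, and a failed check replaces the only named between-arm model with Friedman's test, which cannot compare arms

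*Combined protocol and SAP*

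**What the plan says.** In STATISTICS, item 2 (Statistical analysis plan), the analysis is set out in two steps. First: "Mixed models ANOVA will be used to show effect of time on pain score and also to evaluate group interaction". Then, under non-parametric tests, Friedman's "test will be used if data did not show normal distribution". The section closes with "Significance level will be considered at 0.05". It names no normality test and no level for one. It does not define the data to be judged, and it names no rank-based comparison between groups.

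Three other places bear on this:

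- STATISTICS, item 1 (Sample size estimation) works "with a background standard deviation of 1.0" and a "significant reduction in VAS defined as at least 50% reduction". It then raises the size to 27 per group as a non-parametric correction, so the fallback is treated as a live prospect.
- Inclusion criterion 2 requires unsatisfactory control on oral drugs "including strong opioid with VAS >5", which cuts off the baseline score from below.
- OUTCOME AND ASSESSMENT lists four instruments as primary (VAS, ODI, QLQ-C30, QLQ-BM22), so the switch could go differently for each.

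**The concern.** There are two separate faults.

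1. **The consequence of switching.** Friedman's test compares repeated measurements within patients. Applied to this trial it answers whether scores change over time, not whether the arms differ. The mixed ANOVA is the only named analysis with a group term, so following the rule as written can remove the comparison for which patients were randomized.

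2. **The trigger.** The mixed ANOVA assumes roughly normal residuals. Raw scores need not be normal for it to be valid. Scores pooled over arms with different means are a mixture, and baseline scores are truncated by the entry rule. Repeated checks also fail by chance. None of these shows that the model is unsound, yet each could trigger the switch if raw scores are what is judged.

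At stake is whether the reported primary result is a between-arm result at all. That would be settled after the outcomes are seen, by a rule not written down.

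**Working it through.** **Inputs from the documents.** Three arms of 27 (81 in total); SD 1.0; target of at least a 50% fall in VAS; entry VAS above 5. PATIENTS AND METHODS gives four assessments (baseline, 1, 3, 6 months) in its opening text and five (adding 3 days) where the instruments are described.

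**Assumptions.** VAS on a 0-10 scale, Shapiro-Wilk at 0.05, normal scores within arm, two-sided tests. The documents give no between-arm gap, no baseline mean and no within-patient correlation.

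**The plan's own figure.** It gives no switching rate; its nearest figure is 25 per group. With n = 2(1.960 + 0.842)²·SD²/gap² and SD 1.0:

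- gap 0.8: 2 × 7.85 / 0.64 = 24.5, so 25 per group;
- gap 2.5 (half of a VAS of 5, control unchanged): 2 × 7.85 / 6.25 = 2.5, so 3 per group.

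The 25 is matched only by a back-solved gap of 0.8, while the stated 50% target implies at least 2.5. Both are therefore carried through below.

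**Reading A: raw scores pooled over arms at one visit.** Both active arms are shifted equally from an unchanged control, SD 1.0.

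| Gap (points) | Pooled raw scores fail | Residuals fail |
|---|---|---|
| 0 | about 5% | about 5% |
| 0.8 | about 5% | about 5% |
| 2.0 | 15% | about 5% |
| 2.5 | 38% | about 5% |
| 3.0 | 74% | about 5% |
| 3.6 | 97-98% | about 5% |

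The 3.6 row is a 50% fall from an assumed baseline of 7.2. Varying that row:

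- control also improves by 1.5 points (gap 2.1): about 18%, give or take two points of simulation error;
- active arms fall by 1.8 and 3.6: about 16%;
- SD 2.0, scores not bounded: 10%;
- SD 2.0, scores clipped to 0-10, control mean 7.2: 29%, against about 67% with no effect at all, so the direction reverses.

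**Reading B: each arm at each visit, any one failure counts.** For truly normal data and independent tests, the chance of at least one failure is 1 − 0.95^k:

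- 3 arms × 4 visits: 1 − 0.95^12 = 46%;
- 3 arms × 5 visits: 1 − 0.95^15 = 54%.

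With correlated visits, simulation gives about 45% and 51-54%. At a single visit, the chance that any of the three arms fails is 13-15% whatever the treatment effect.

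**Entry cut-off (baseline only).** All 81 pooled, normal scores truncated to 5-10. Failure rates by mean and SD before truncation:

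- mean 7, SD 1.0: 8%
- mean 6.5, SD 1.0: 33%
- mean 6, SD 1.0: 79%
- mean 7, SD 2.0: 69%
- mean 6, SD 2.0: 93%

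**What a switch costs.** Whole-trial simulation with four visits, correlation 0.5, baseline mean 7 and SD 1.0 cut at 5. The switch occurs if pooled raw scores fail at any visit. Group-by-time is approximated by a one-way ANOVA on the change from baseline to the mean of the follow-up visits.

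| Gap (points) | Significant group-by-time, no switch rule | Model kept and group-by-time significant |
|---|---|---|
| 0.8 | 97% | 77% |
| 2.0 | 100% | 59% |
| 3.5 | 100% | 0.1% |

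When all three arms fall by the same 2 points, Friedman's test on all patients rejects in 100% of trials and the group-by-time test in 5%. A significant Friedman result therefore says nothing about the arms.

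**The case against.** The strongest reply is that the text says only that the data are judged. It does not say raw scores, and it names no formal test. An analyst who inspects residuals would not see the effect-driven trigger, and checking arms separately makes the trigger independent of the effect. The general reference to non-parametric tests might also be meant to include a between-group test. This stands as far as it goes: readings A and B are possible, not established. It does not rescue the rule, because no between-arm alternative is named and nothing directs the analyst to residuals.

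A reader might infer more than the documents support:

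- *That a larger true benefit always makes the switch more likely.* This needs raw scores pooled over arms, SD near 1.0 and a gap of about 2 SD or more. It is absent at 0.8 points and weak if control improves or the active arms differ. At SD 2.0 with bounded scores it reverses. The control arm receives local anesthetic with identical needle placement, so an unchanged control cannot be presumed.
- *That the 97-98% follows from the plan's own inputs.* Only SD 1.0 and the 50% target do; the 7.2 baseline and unchanged control are assumptions.
- *That the entry cut-off will trigger the switch.* It bears on baseline only and is near nominal at SD 1.0 and mean 7.
- *That the choice is made on unmasked data, or that the 0.05 level is inflated.* The documents do not say whether the analyst is masked, and no type I error for the two-stage procedure has been calculated here.

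**Conclusion.** The point holds as a fault in the rule, beyond mere missing detail. Followed as written, it can leave the trial with no named between-arm test, and that conclusion needs no simulation. How often this would happen cannot be fixed from the documents. Under the readings examined, it runs from about 5% for a single pooled check with little or no effect, through about 45-54% for cell-by-cell checks on normal data, to 97-98% for a pooled check at one visit with a 3.6-point gap at SD 1.0. The last figure rests on the most favourable assumptions for the concern and should not be quoted without them. The flat 5% for residuals likewise assumes normal, unbounded scores within arm. This should be corrected, but it does not show that the trial's conclusions are wrong.

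**What to change.** Delete the normality switch from the Statistical analysis plan. In its place:

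- name the mixed model with group, time and group-by-time as the primary analysis for each of the four instruments, whatever the raw distribution, and list the between-arm contrasts to be reported;
- state that its residuals, not the raw scores, will be inspected;
- state that a permutation or bootstrap p-value for the same between-arm contrasts will be reported in all cases as a sensitivity analysis.

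Friedman's test, if kept, should be labelled as a description of change over time within patients. The cost is about two sentences and a little more analysis, with no change to data collection or sample size.
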